2.3. Rationale for Dosage

Subjects will be treated with Pioglitazone 30 mg po daily when on treatment, following an initial 2 week period to assess tolerability, particularly in patients with stage 1 or stage 2 heart failure. Pioglitazone was selected because of our recent investigations showing its profound efficacy in decreasing proliferation in human SCC in vitro (see BACKGROUND). The oral dose selected results in serum levels of Pioglitazone that correspond to the in vitro dose tested in our studies(Christensen *et al.*, 2005). In addition to the drug itself acting as an agonist for PPAR γ , there are 2 persistent metabolites that have similar agonist effects, increasing the possibility of tumor growth inhibition. Thus, this dosing regimen is likely to give optimal suppression of tumor growth. This is a standard dose (30 mg) taken by patients who are taking Pioglitazone for management of their diabetes. When given to non-diabetic patients with non-alcoholic liver disease or those with hepatitis C to prevent cirrhosis(Bell *et al.*, 2012), there were no untoward effects on glucose metabolism.

3. CHARACTERISTICS OF THE RESEARCH POPULATION

3.1. Subject Characteristics

a) Number of Subjects:

Forty subjects will be recruited to participate in this protocol. It is expected that we will have 1 screen failure for every 4 subjects consented (mostly due to onset of other complex disease unrelated to their skin). There are no other participating sites.

b) Gender and Age of Subjects:

Adult subjects of both genders will be recruited. However, high frequency of SCC is more common in men, and the balance of patients recruited to the study will reflect this. SCC is a disease of older individuals, usually 50 and up, unless they are transplant recipients or have a genodermatosis that predisposes them to multiple tumors. This disease is virtually unknown in pediatric patients, so patients < 18years will be excluded.

c) Racial and Ethnic Origin:

Squamous cell carcinoma in skin is induced by chronic exposure to ultraviolet light. Individuals who have dark skin pigmentation are highly resistant to this disease, so the study population will be largely Caucasian. Most Hispanic individuals are also too darkly pigmented to suffer from this condition because of the capacity of their skin to tan.

3.2. Inclusion and Exclusion Criteria

a) Inclusion Criteria:

- >18 years of age, male or female, state of health stable
- Able understand protocol and give consent
- Has had treatment of 2 – 6 squamous cell carcinomas of the skin during the year prior to enrollment, & pathology is available for verification
- Stable treatment regimen for their skin cancer problems in place for 1 year, with expectation to keep medications the same during study
- Able to keep study appointments & comply with protocol

b) Exclusion Criteria:

- Unwillingness or unable to complete informed consent process
- < 18 years of age
- Allergy to Pioglitazone
- Taking Rifampin, Trimethaprim, Celebrex or Gemfibrozil
- Pregnant or breastfeeding (Pregnancy Category C)
- History of heart failure NYHA Class III or Class IV
- Subjects with type 1 or type 2 diabetes
- Problems with pedal edema
- Liver disease (ETOH, viral hepatitis, drug-induced hepatitis) or elevated ALT, AST or total bilirubin
- Osteoporosis with high risk of fracture
- History of bladder cancer
- Recent change in chronic oral medications. Participants enrolled while on a systemic medication for their skin cancer must remain on treatment.

3.3. Vulnerable Subjects

We will not be recruiting vulnerable subjects.

3.4. Discussion of Subject Population

Patients with diseases that are likely to be made worse by Pioglitazone are excluded (heart failure, liver disease, osteoporosis or bladder cancer). Patients must have had a sufficient number of prior tumors that their increased risk of developing tumors in the future is clear.

4. SUBJECT IDENTIFICATION, RECRUITMENT AND CONSENT

4.1. Method Of Subject Identification And Recruitment

Patients receiving care at the University of Rochester Department of Dermatology for their squamous cell cancer who meet study inclusion criteria will be asked by Dermatologic surgeon [name] about their interest in study participation. Subjects will be given the consent

form to examine and the contact number for the study coordinator, [name], who is approved to enroll subjects. [name] will have no involvement in the consenting process for individuals he sees as a patient. It will be made clear to the potential subjects that their participation is voluntary and their care in the Department of Dermatology will not be affected by their decision to participate in this study.

To further enhance enrollment, a “Dear Colleague” Letter may be sent to Dermatologists and Mohs surgeons in the Rochester area who work at sites other than Red Creek, or refer patients to the University of Rochester Department of Dermatology in order to recruit subjects. For those faculty employed full-time at the University of Rochester, who see potential study subjects in our Dermatology practice, a prescreening process will also be conducted by study coordinator [name]. She will review the EPIC records of potential subjects coming for appointments to see if they meet eligibility criteria. If a patient coming to a visit meets study criteria, a bright pink reminder sheet titled “Inclusion-Exclusion Criteria Pioglitazone Pink Sheet” outlining the key aspects of the study and its inclusion and exclusion criteria will be placed with the intake form. This visual reminder to employed faculty that the patient they are about to see may be eligible to participate is intended to facilitate their asking the patient about their interest in the study. Faculty will then be able to let the patient know about the study and ask if the patient has an interest in being contacted by the study coordinator. If the potential subject shows interest, the study coordinator will contact them by phone to further explain the study. Interested subjects will be mailed the consent form and a date arranged for them to come to the office to formally review the consent document and give their consent. Again, it will be made clear to the potential subjects that their participation is voluntary and their care in the Department of Dermatology will not be affected by their decision to participate in this study.

4.2. Process of Consent

[name] or the coordinator will meet with interested subjects in a private room. The consent form will be read in its entirety by the subject. Time allotted to consenting will be dependent on the subjects’ needs, questions, and comprehension of the information in the consent form. Each subject will be encouraged to read the consent form on his/her own and ask any specific questions.

At the time of consent, subjects will be offered the option to provide permission to be contacted in the future regarding this and other dermatologic studies. Those who provide permission for future contact will be added to a list of high risk squamous cell skin cancer patients that are interested in participating in clinical research.

Subject Capacity

We will not be recruiting subjects incapable of giving informed consent. The subject’s capacity to comprehend the information in the consent form will be assessed by asking questions about the content and encouraging the subject to describe the study procedures.

Documentation of Consent

The participant’s consent will be documented by signing the consent form by both the study subject and the person obtaining consent.

5. METHODS AND STUDY PROCEDURES

A schedule of study visits is provided in Appendix 1. A description of the study procedures are also listed in appendix 1.

Outlined below are the assessments that will be performed to evaluate efficacy and those to evaluate safety. Tests and interventions which are considered experimental and performed exclusively for research purposes have been identified and differentiated from that which would occur regardless of the research (i.e., standard of care).

5.1. Efficacy Assessments

Administration of Pioglitazone to prevent/decrease the aggressive phenotype of skin cancer is experimental. NB- obtaining biopsy of lesions suspected of skin cancer is NOT experimental; it is required for usual patient care in these high risk patients. In order to know whether Pioglitazone is efficacious for preventing SCC in high risk individuals, we will count the number of skin tumors documented by biopsy/treatment that occur in our subjects before, during, or after Pioglitazone treatment. This assessment will take into account compliance, as described below. The tumor counts will be best interpreted in aggregate for the whole sample group, since there is variability in the frequency with which new tumors appear based on the predisposing condition. Since Pioglitazone has been on the market for some time without observation of a negative impact on skin or wound healing, the study focus will be determining if numbers of tumors decrease and whether their phenotype changes. The physician reading the pathology of the skin biopsies will be responsible for identifying the number of tumors that occur –i.e., some lesions thought to be tumors and therefore biopsied in clinical practice turn out to be hypertrophic actinic keratosis (not tumors). These would not be counted as skin cancers, since they are precancerous lesions.

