2. STUDY DESIGN

2.1. Overview

This is a single center open label feasibility pilot project based at the University of Rochester. Patients followed in the University of Rochester Dermatology Clinic who have had between 2 to 6 squamous cell cancers treated in the past year, without contraindication for the use of Pioglitazone, and are on a stable drug treatment regimen will be offered participation. The study has a cross-over design, so patients will be enrolled and randomized in one arm of two treatment protocols: 1) six months of usual care while documenting and characterizing any new tumors that occur followed by 6 months of Pioglitazone treatment plus usual care for the next 6 months or 2) six months of Pioglitazone treatment followed by 6 months off treatment receiving usual care (see protocol diagram, Section 5, below). The second group will offer the opportunity to assess whether there is any persistent beneficial effect after pioglitazone treatment ends, while tumors from the first group that occur during the initial 6 months of usual care will be characterized by study parameters for comparison to tumors arising while on treatment. At the end of the one year treatment period, the number of new tumors that patients develop while taking Pioglitazone will be counted and compared with the number that patients developed during the 6 month period they were not receiving treatment as well as the numbers that occurred during the 6 months after treatment (washout effect). This information will be used as the basis for a larger multicenter study.

[figure not shown]

Fig 2. Schematic for the Proposed Study (study visit day are +/- 7 or 14 days)

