This study will also assess secondary endpoints. First, we will examine whether the ratio of well-differentiated to poorly differentiated SCC is influenced while subjects are on treatment. This endpoint is included because it is unknown whether there may be more signaling mediated by PPAR γ in one tumor morphology vs. another. Second, we will determine whether patients on treatment might have different numbers of “borderline” lesions biopsied; precancerous lesions are often suspicious enough to biopsy. It may be that there will be fewer lesions in this category, as well as fewer squamous cell cancers. Third, we will test tumors that are excised after they are processed for routine diagnostic pathology to see if markers of proliferation or apoptosis that are influenced by PPAR γ activity or the presence of AKR1C3 are altered. These endpoints would support the idea that any changes produced in tumor incidence while patients are on study drug are related to the mechanistic effect on PPAR γ that is proposed.

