5.8. Return of Individual Research Results

Any side effects suspected to be related to the study drug will be reported to the subject at the time of their detection. Subjects who have significant side effects attributable to study drug will be dropped from the study, and the side effects reported to their physician. Since the study is not blinded, subjects will be directly aware of whether there is a detectable difference in the incidence of their skin cancers.

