12. RESEARCH INFORMATION IN MEDICAL RECORDS

Blood test results will be in the patients' medical record for medical reasons unrelated to Pioglitazone treatment, as will results of biopsies as needed for normal patient care. No other study information will be in the medical record.

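### In an open-label trial, the physician whose biopsy reading sets the primary tumor count is not required to be unaware of treatment or period

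*Combined protocol and SAP*

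**What the plan says.** Section 2.1: "This is a single center open label feasibility pilot project based at the University of Rochester". Section 5.8 confirms that patients are not masked: "Since the study is not blinded, subjects will be directly aware" of any change in their skin cancer incidence.

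Sections 13.1 and 13.2 make the number of skin tumors in each treatment period the primary endpoint.

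Section 5.1 says who decides that number: "The physician reading the pathology of the skin biopsies will be responsible for identifying the number of tumors that occur". It also names the difficult call: "some lesions thought to be tumors and therefore biopsied in clinical practice turn out to be hypertrophic actinic keratosis". Those lesions are treated as precancerous and left out of the count. Section 2.2 adds that "precancerous lesions are often suspicious enough to biopsy", and lists the number of such borderline biopsied lesions, and the ratio of well to poorly differentiated SCC, as secondary endpoints.

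Taking the biopsy belongs to usual care: "obtaining biopsy of lesions suspected of skin cancer is NOT experimental" (section 5.1). No biopsy threshold and no masked examiner are described.

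Two statements bear indirectly on what a reader could learn. Section 11 lists random coded labels for samples and data among its confidentiality measures. Section 12 says that blood and biopsy results will be in the chart, and then: "No other study information will be in the medical record".

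**The concern.** Randomizing the order of treatment and comparing each patient with himself or herself protects against differences between patients. It does not protect against an assessment that follows the treatment. If doubtful lesions are read a little more leniently in the pioglitazone period, in both arms, the difference goes straight into the treatment contrast.

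The conditions for this are present. The count depends on a histologic judgment at a boundary that the protocol says is met often. The trial is open label. Section 2.2 hypothesizes a reduction of more than 50%, so the direction of any expectation is predictable. No sentence in the supplied text keeps treatment or period from the reader.

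The stake is both the test and the estimate. Section 2.1 says that the results will be the basis for a larger multicenter study, so an inflated effect would pass into that study's sample size. The differentiation endpoint is also a histologic judgment and is exposed in the same way.

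**Working it through.** **1. Is there a masking rule?** The relevant sections, side by side:

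| Section | Content | Does it mask the reader? |
|---|---|---|
| 2.1, 5.8 | Open label; patients know their treatment | No |
| 5.1 | Reading physician determines the count | No condition attached |
| 11 | Coded labels, for confidentiality | Not stated to apply to the diagnostic reading |
| 12 | Little study information in the chart | May limit disclosure; does not forbid it |
| 13.2 | Analysis of counts | No second reading or adjudication |

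Section 2.2 says that marker tests are done after tumors have been processed for routine diagnostic pathology. Nothing shows that the coding in section 11 governs that earlier diagnostic reading.

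**2. The plan's own figure.** Inputs from section 13.1: N = 40, difference 0.75, within-patient SD (Sw) 1, two-sided 5%.

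- SE = Sw × √(2/N) = 1 × √(2/40) = 0.2236.
- Noncentrality = 0.75 / 0.2236 = 3.354, with 38 degrees of freedom.
- Power = 90.5%, not the stated 96%.

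That mismatch is a separate matter and does not bear on this point. The same formula is used below.

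**3. Illustration: the whole SCC count is lower on drug.** Assume no true effect and 1.5 tumors per period on usual care (section 13.1). Through reading or biopsy choice, the count on drug is lower by a fraction m. The documents give no value for m. Take Poisson variation, so Sw = √(average of the two means).

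| m | Mean on drug | Difference | Sw | SE | Noncentrality | Rejection |
|---|---|---|---|---|---|---|
| 10% | 1.350 | 0.150 | 1.194 | 0.267 | 0.562 | 8.5% |
| 15% | 1.275 | 0.225 | 1.178 | 0.263 | 0.854 | 13.2% |
| 20% | 1.200 | 0.300 | 1.162 | 0.260 | 1.155 | 20.3% |

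With the plan's Sw = 1, the rejection rates are 10.0%, 16.5% and 25.8%. A simulated Poisson comparison of totals, closer to the model in section 13.2, gives 8.4% at m = 10% and 20.6% at m = 20%. In lesions, 40 × 1.5 = 60 tumors are expected per condition, so these shifts are 6, 9 and 12 lesions across the trial.

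**4. Illustration: only borderline calls shift.** Let f be the share of counted SCCs that are borderline; this too is an assumption. The total then falls by f × m. For example, f = 30% and m = 20% gives 0.30 × 0.20 = 6%, a difference of 0.09.

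| f | m = 10% | m = 15% | m = 20% |
|---|---|---|---|
| 10% | 5.0% | 5.1% | 5.1% |
| 20% | 5.1% | 5.3% | 5.5% |
| 30% | 5.3% | 5.7% | 6.2% |
| 50% | 5.8% | 6.9% | 8.5% |

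**5. Effect on the estimate.** If the total on drug is undercounted by 20%, a true 50% reduction appears as 1 − 0.50 × 0.80 = 60%, and a true 25% reduction as 1 − 0.75 × 0.80 = 40%.

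**The case against.** The strongest reply is that the readings are ordinary diagnostic pathology within usual care, that samples are coded, and that the chart carries almost no study information. A routine reader may never learn the assignment. This is also a departmentally funded pilot, and section 2.2 gives reasons for the open-label crossover.

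Much of this stands. Sections 11 and 12 make disclosure less likely, and Appendix 1, which describes the study procedures, is not in the supplied text. But neither section states a requirement. The reasons in section 2.2 (pilot aim, funding, recruitment) may explain an open-label trial; they do not explain leaving the reader unmasked, since masking the reader needs no placebo and no extra patients.

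Some stronger readings are tempting and are not supported:

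- **That readers know the treatment, or that one reader makes every call.** The documents say neither, and they do not describe what accompanies a biopsy to pathology.
- **That leniency on borderline lesions alone would push false positives to 20%.** That figure needs the whole SCC count to fall by 20%. With the shift confined to borderline lesions, inflation is slight unless they are a large share of SCCs.
- **That the plan has no check at all.** Section 2.2 already plans to compare borderline lesions biopsied. What is missing is an analysis of that endpoint in section 13.2.
- **That counting biopsies by period would show whether biopsy practice was biased.** Section 2.2 allows that an effective drug may reduce borderline lesions as well as SCCs, so fewer biopsies on drug could be bias or benefit.

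**Conclusion.** The point holds as a gap in outcome assessment. In the supplied text, the primary count depends on a judgment between SCC and hypertrophic actinic keratosis, and the physician making it is not required to be unaware of treatment or period. The documents establish that bias is possible; they do not establish that it occurs or how large it is.

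The size rests entirely on assumed shifts. A total count 10% to 20% lower on drug raises the false-positive rate from 5% to about 8.5% to 20%. Shifts of that size in borderline calls only, at 30% to 50% of SCCs, give about 5% to 8.5%. Even at the low end the change is worth making, because it costs little and the estimate is meant to inform a larger trial.

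**What to change.** **Section 5.1.** State that the physician reading the biopsies is masked to study arm, period and drug, and that material sent with the biopsy carries none of this information. If Appendix 1 already says so, refer to it here. This uses the existing reader and also protects the differentiation endpoint.

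**Section 13.2.** As a secondary descriptive step, report the borderline lesions already planned in section 2.2, by treatment arm and period, beside the SCC counts. A fall in SCC with a matching rise in borderline lesions on drug would point to a shift between categories. The table cannot by itself separate a changed biopsy threshold from a drug effect, and the text should say so.

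**Cost.** Two sentences, minor handling work on biopsy paperwork, and one table for an endpoint already planned. No sample-size figure changes. What remains is that the choice of which lesions to biopsy stays unmasked, which should be acknowledged as a limitation when the results are reported.

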5.2. Safety Assessments

The main safety issue associated with this trial is whether an adverse effect will occur in patients due to the administration of pioglitazone. Clinical endpoints to monitor for safety are: weight, pedal edema, dyspnea, heart failure, headache, myalgia, fracture, liver injury and vision changes related to macular edema, blood in the urine or other changes that are out of the ordinary. The study related blood monitoring is to ensure there are no preexisting conditions that make participants susceptible to drug-related side effects. For instance, individuals with preexisting liver disease may have hepatotoxicity when taking pioglitazone, hence they must be excluded from participation. However, since participants could develop new diseases while participating, blood will also be taken from subjects taking pioglitazone to screen for such concerns. At a study visit approximately 60 days after drug initiation, blood work will be repeated to detect changes suggesting drug related side effects. Monitoring of blood for glucose levels, altered liver function, or decreased Hemoglobin could indicate the patient should stop taking the study drug. Tests to be followed will be CBC and CMP at baseline, approximately 60 days after starting drug and at the end of treatment. Blood test results will be interpreted in the context of the clinical exam. The patient population being studied has co-morbidities that require them to regularly give blood to monitor their health as part of their routine care, so study related blood draws may not be necessary if these tests are obtained by their providers at appropriate intervals; it will not be necessary to repeat them. The risk of bladder cancer will be monitored by urinalysis. Taking Pioglitazone for > 1 year increases the risk of bladder cancer from 7 in 10,000 to 10 in 10,000. Female patients of child bearing age will have urine pregnancy testing at baseline and at subsequent study visits. **Stop Criteria:** Subjects will be

dropped from the protocol if clinical or laboratory assessment reveals grade II abnormalities as defined by Common terminology Criteria for adverse events V.3. Subjects will also be dropped from the protocol if they are unable to tolerate 30 mg Pioglitazone treatment when the dosage is increased to 30 mg daily after the initial 2 week treatment with 15 mg daily.

